# C. Dosimeter Badge Positions

Prior to each catheterization procedure the radiation badges will be placed at each location by the research coordinator, radiation safety officer, or trained cath lab staff member. The dosimeter badges will be removed at the end of each case. The location of the badges is shown below:

	RaySafe	Landauer
	(Dose Per Case)	(Cumulative Dose)
Primary Operator	Thyroid	Thyroid (2)
	Knee	Inner (2)
Secondary Operator	Thyroid	Thyroid (2)
	Knee	Inner (2)
Nurse	Thyroid	Thyroid (2)
	Knee	Inner (2)

Cath Lab	Wall	Wall (2)

The outer dosimeter badges will be placed on the left anterior side of the thyroid collar and the left ankle. The knee badge is affixed to the lower seam of the lead apron.

The inner badges will be placed underneath the lead apparel over the left anterior chest.

The cath lab dosimeters will be placed at standard location on the wall at the foot end of the cath lab table.

For the Landauer dosimeters, two badges will be placed at each location (one badge as a backup). 28 badges will be required (14 with and 14 without ControlRad)

4.5 Radiation Settings in Lab

The frame rate for fluoroscopy will be 7.5 frames per second (fps) and 15 fps for cineangiography (these settings are currently the default in Lab 5).

4.6 Catheterization Procedure and EP procedure

Cardiac catheterization, percutaneous coronary intervention, pacemaker and ICD implantation will be performed according to standard guidelines and clinical practice. The ControlRad is only used during fluoroscopy (the device is not used during "cine" acquisition runs). In the event use of the ControlRad device is felt to significantly diminish imaging quality outside the region of interest the device can be turned off. Standard of care views (typically orthogonal) will be performed after PCI to ensure there is no vessel injury.

Each attending physician may perform 1-2 "roll-in" cases to train on the ControlRad system before randomizing patients in the study.

Follow-Up
No clinical follow-up will be performed after the hospital stay since the primary endpoint is radiation dose measured in the cath lab.

#### 5.0 Data Management

- 5.1 Data Collection Data will be collected in case report forms in the REDCap database.
- 5.2 Effective Radiation Dose The effective radiation dose per case (E) will be calculated using a single dosimeter method (8).

# 5.3 Power Analysis

In 2017, the median total air kerma dose (TAK) for a diagnostic and PCI in Cath Lab 5 was 460 mGy and 1577 mGy respectively. Approximately 50% of the TAK for a diagnostic or PCI procedure is from fluoroscopy and 50% from cineangiography. In pre-clinical studies the ControlRad system reduced radiation dose by 75% during fluoroscopy. Using PASS 14 Power Analysis and Sample Size Software (2015). NCSS, LLC. Kaysville, Utah, USA, ncss.com/software/pass, we found that 9 diagnostic patients and 6 PCI patients per arm would give us 80% power to detect that absolute difference of 20% with a 0.05 significance level. Allowing for some variation in the actual frequencies in this higher risk group of patients or any drop outs, we intend to enroll 30 patients per arm.

#### 5.4 Blinding

The physicians and nurses will be blinded to the radiation dose received in each case. The radiation dose to each operator and nurse will be recorded after every case by the study coordinator or radiation safety operator.

#### 5.5 Statistical Analysis

Data will be analyzed on an intent-to-treat basis. Continuous variables will be reported as mean  $\pm$  standard deviation, and where appropriate as median  $\pm$  interquartile range. Analyses will be performed by a biostatistician using with SAS software for Windows version 9.3 (or higher).

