#### 1.0 Protocol Summary

Title	A prospective, randomized evaluation of the ControlRad system to reduce radiation exposure during cardiac catheterization and electrophysiology procedures		
Design	Prospective, randomized, single center evaluation		
Procedure	40 cardiac interventional procedures and 120 pacemaker and/or ICD procedures		
Objective	To determine whether the ControlRad system reduces radiation exposure to operators, staff and patients during diagnostic and interventional cardiac catheterization procedures and electrophysiology implant procedures		
Enrollment	Prospective		
Site(s)	Beaumont Hospital Royal Oak		
Time Course	2020- 2021		
Primary Outcome	Effective radiation dose to primary operator		
Principal Investigator	r [name]		
Co-Investigators	[name], [name], [name] Study Coordination Beaumont Hospital Royal Oak		

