# 2.0 Background

# 2.1 Current Approaches for Radiation Protection

Long-term radiation exposure in the cardiac catheterization laboratory is associated with an increased risk of premature cataract formation, chromosomal damage, subclinical atherosclerosis and cancer (1-4). Conventional approaches to limit radiation exposure include a) wearing lead apparel, b) positioning table and ceiling-mounted radiation shields between the operator and patient, and c) technical considerations such as reducing the fluoroscopic frame rate, minimizing fluoroscopic time and acquisition runs, maintaining the optimal table height and image intensifier position, and use of filters and collimators in the imaging chain (5,6).

Despite these approaches, physicians working in the cardiac catheterization laboratory continue to receive high doses of radiation, primarily attributable to scatter radiation from the patient. This situation has in part been compounded by the increasing complexity of therapeutic procedures, such as interventions for chronic total occlusion. Prior studies have demonstrated that the primary operator is subject to the highest radiation dose due to proximity to the primary radiation beam, but other operators and staff also receive significant occupational exposure. Because of these concerns, there

has been a clear need to develop new methods to reduce radiation exposure to physicians and staff in the cardiac catheterization laboratory.

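### The planned dose comparison ignores patient size, which Table 1 already collects: a loss of precision of unknown size, not a bias

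*Combined protocol and SAP*

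**What the plan says.** The primary outcome in section 1.0 is "Effective radiation dose to primary operator". Section 3.6 defines it as a mean in µSv, and section 5.2 derives it per case.

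Section 5.5 is three sentences long. It says "Data will be analyzed on an intent-to-treat basis. Continuous variables will be reported as mean" with SD, or median with IQR where appropriate, and then names the software. There is no test, model, covariate or transformation.

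Weight, height, BMI and BSA appear only as rows of the Table 1 shell. Table 3, the shell for per-case badge doses, has two arm columns and a p-value, with no adjusted estimate. Section 4.3 randomizes 1:1 and names no stratification factor, so size does not enter through the design either.

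Section 2.1 describes the dose to physicians as "primarily attributable to scatter radiation from the patient".

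**The concern.** If operator dose is mainly scatter from the patient, the size of the scattering body is a natural candidate predictor. It is known before allocation and cannot be affected by the device. It also differs from procedure type and from operator: two patients having the same procedure with the same operator can still differ in size. A comparison that ignores size leaves whatever variation it explains in the standard error of the device effect. At stake is the trial's ability to detect a dose reduction, and to estimate it closely, with the cases it has.

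**Working it through.** **Inputs from the documents.** Section 5.3 gives alpha 0.05, 80% power, 9 diagnostic and 6 PCI patients per arm, 30 per arm to be enrolled, and median total air kerma of 460 mGy (diagnostic) and 1577 mGy (PCI). Sidedness is not stated; two-sided is used here. No SD or CV of dose and no size–dose correlation appears anywhere.

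**Assumptions.** Within-class correlation r of size with log dose: 0, 0.3, 0.5, 0.6. For step 3 only: a one-third PCI share (in line with the 2:1 ratio in section 3.3), a within-class SD of log dose of 0.4 to 0.8, and patient air kerma standing in for operator dose.

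**1. The plan's own figure.** Section 5.3 says its numbers "would give us 80% power to detect that absolute difference of 20% with a 0.05 significance level". With no SD, this can only be solved backwards. From n = 2 × 2.8016² × (CV/d)², CV = d × √(n/2) / 2.8016. At d = 0.20:
- n = 9: 0.20 × 2.121 / 2.8016 = 0.151 (0.142 by noncentral t)
- n = 6: 0.20 × 1.732 / 2.8016 = 0.124 (0.111)
- n = 30: 0.20 × 3.873 / 2.8016 = 0.276 (0.272)

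The stated sizes therefore cannot be confirmed. The 80% used below is a reference point, not the plan's claim at 30 per arm.

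**2. Gain when procedure class is also in the model.** Residual variance is multiplied by 1 − r². Power = Φ(2.8016/√(1 − r²) − 1.96).

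| r | 1 − r² | Equivalent extra cases, 1/(1 − r²) − 1 | Argument of Φ | Power | Simulated, 30 per arm |
|---|---|---|---|---|---|
| 0.3 | 0.91 | 10% | 0.977 | 84% | 82% |
| 0.5 | 0.75 | 33% | 1.275 | 90% | 88% |
| 0.6 | 0.64 | 56% | 1.542 | 94% | 93% |

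The simulation (6,000 runs per setting) gave 78–80% unadjusted, and about 78% adjusted at r = 0. If size is unrelated to dose, the cost is one degree of freedom, about 1 percentage point of power.

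**3. Gain when class is left out.** log(1577/460) = 1.232. The between-class variance is 1.232² × (1/3) × (2/3) = 0.337, and adjusting for size does not remove it. At r = 0.5:
- Within-class SD 0.4: (0.16 × 0.75 + 0.337)/(0.16 + 0.337) = 0.92; power about 83%
- Within-class SD 0.8: (0.64 × 0.75 + 0.337)/(0.64 + 0.337) = 0.84; power about 87%

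The same calculation gives 81–82% at r = 0.3 and 85–89% at r = 0.6.

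**4. Chance imbalance in size.** At 30 per arm, the arm difference in mean size has SD √(2/30) = 0.258 patient-size SDs. At r = 0.5 this moves the estimate by 0.5 × 0.258 = 0.129 dose SDs, against an unadjusted standard error of 0.258 dose SDs. (0.129/0.258)² = 25%, which is exactly the variance reduction in step 2.

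**5. What this means at 30 per arm.** For a 20% difference and r = 0.5, power goes from 72% to 83% at an assumed CV of 0.3, from 33% to 42% at 0.5, and from 12% to 14% at 1.0.

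**The case against.** The strongest reply is that the missing covariate is a detail of a larger gap: section 5.5 specifies no primary analysis at all. The source of variation that the documents do quantify is procedure class, with a 3.4-fold difference in median air kerma. Patient size is not quantified. Section 2.1 speaks of scatter from the patient, not of patient size, and also lists shields, frame rate, fluoroscopy time, table height and collimation as influences on exposure. All of this stands. It makes the gain uncertain and ties it to having class in the model. It does not remove the case for the covariate, because size varies within class and costs almost nothing to include.

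A reader might infer four stronger things that the documents do not support:
- **That the unadjusted result is biased.** It is not. Randomization protects it, and its standard error already covers chance differences in size.
- **That residual noise and chance imbalance are two harms.** Step 4 shows they are one. With about 200 catheterization or 120 EP patients (section 3.3), that is 100 or 60 per arm, the imbalance SD would be 0.14 or 0.18 rather than 0.26, but its share of the variance is unchanged.
- **That size is recorded for every case.** Table 1 is headed N=60, with diagnostic, PCI and access-site rows and none for pacemaker or ICD. Recording in the EP cases is an inference.
- **That one sentence naming a covariate is enough.** There is no model to add it to, and a log scale would change the estimand from the mean dose of section 3.6 to a ratio of geometric means.

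**Conclusion.** The point holds as a precision gain of unknown size. The plan collects a plausible predictor that is fixed before allocation and does not use it in the comparison the shells imply. Validity is not in question.

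The figures of 84%, 90% and 94% rest on assumed correlations, on a reference power of 80%, and on procedure class being in the model; the simulated values at 30 per arm run 1 to 2 points lower. Without class the gain is clearly smaller. The downside at r = 0 is slight, so the change is worth making when the primary analysis is written, but it does not rank above specifying that analysis and including class.

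**What to change.** In section 5.5, name the primary model for per-case primary-operator effective dose. Prespecify in it one pre-allocation size measure (BMI or weight) as a continuous covariate, together with procedure class. One measure is enough, since weight, BMI and BSA largely overlap; naming it now also prevents a choice made after seeing Table 1. Use the same terms for the other per-case dose endpoints and for DAP. They cannot be applied to the Landauer badges, whose readings are cumulative over cases.

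If dose is log-transformed, state that the effect is a ratio of geometric means, and report the arm means that define the section 3.6 endpoint alongside it. Do not adjust for the post-allocation rows of Table 1 (fluoro time, kVp, mA, air kerma, DAP). State when procedure class is recorded, because the documents do not say whether diagnostic or PCI status is always settled before allocation.

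Confirm that the chosen size measure is captured for the EP implant cases. The cost is a short paragraph in 5.5, one degree of freedom for size and those for class, and no new measurement for cases covered by Table 1. If size is not recorded for EP cases, one field must be added to the case report form.

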# 6.0 Risk Analysis

6.1 Risks/Benefits to Physicians and Staff

In the standard of care arm of the study there is no additional risk or benefit to the physicians or staff. In the ControlRad arm there is no risk to the physician or staff however both may benefit from reduced radiation exposure.

6.2 Risks/Benefits to Patient

The decision how to treat the patient is at the discretion of the attending physician. The technical approach used for the cardiac catheterization procedure will not be affected by the ControlRad system. In the standard of care arm of the study there is no additional risk or benefit to the patient. In the ControlRad arm there the patient may benefit from reduced radiation exposure. In the ControlRad arm there may be slightly diminished visualization of surrounding structures (outside the region of interest) when the device is used during fluoroscopy.

# 8.0 Tables

# Table 1. Patient and Procedural Characteristics

	Total	ControlRad	No ControlRad	p-value
	N= 60	N=	N=	
Age				
Weight				
Height				
BMI				
BSA				
Diagnostic				
PCI				
Radial				
Femoral				
Brachial				
Procedure time				
(mins)				
Fluoro time				
(min)				
Detector size				
SID				
Fluoro frame				
rate				
Flouro air kerma				
Fluoro kVP				
Fluoro mA				
Cine frame rate				
Cine magn size				
Cine kVp				
Cine mA				
Total air kerma				
DAP				

	Location	ControlRad	No ControlRad	p-value
		N=	N=	
Operator 1	Thyroid			
	Inner			
Operator 2	Thyroid			
	Inner			
Anesthesia/Nurs	Thyroid			
е				
	Inner			
Cath Lab Fixed	Wall			

# Table 2. Cumulative Radiation Dose Measured with Aluminum Oxide dosimeter badges (mrem)

# Table 3. Mean Radiation Dose to Physicians and Nurse Measured with RaySafe Dosimeters (mrem)

		ControlRad N=	No ControlRad N=	p-value
Operator 1	Thyroid			
	Knee			
Operator 2	Thyroid			
	Knee			
Anesthesia/Nurs	Thyroid			
е				
	Knee
